#### Severity

Assessing the severity of the event according to the following terms and assessments. The intensity of an event should not be confused with the term "serious" which is a regulatory definition based on participant/event endpoint criteria.

- o Mild: Some discomfort noted but without disruption of daily life
- Moderate: Discomfort enough to affect/reduce normal activity
- o Severe: Complete inability to perform daily activities and lead a normal life

# 11.2 Reference Safety Information (RSI)

Reference Safety Information (RSI) is the information used for assessing whether an adverse reaction is expected. Section 9 of the Investigator Brochure details information used for assessing whether an adverse reaction is expected in this trial.

# 11.3 Notification and recording of Adverse Events (AEs), Adverse Device Events (ADEs)

All AE and ADEs are to be documented in the participants' medical notes or other source data documents and the CRF. The period for AE reporting will be from visit one (screening visit) until visit four (day seven). Once assessed, if the AE is not defined as SERIOUS, will not be recorded as an AE on the CRF. AEs must be reported from consent until the participant's last follow-up visit.

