#### 10.12 Management of device-specific adverse events

Any device-specific adverse events (AEs) will be recorded in the patient medical records and eCRF and the information – in pseudo anonymised format – will be passed on to the delegated representative from Afferent Medical Solutions Ltd.

All AEs will be informed to the device manufacturer (Afferent Medical Solution Ltd) as soon as possible after the investigation site staff has become aware of the event. Details of the device-specific adverse will events be sent to the Afferent team on the following email [contact], and where possible, a member of the trial team will contact the Afferent team via phone at [name].

We anticipate following side effects associated with TAN applied via electrical stimulation for the tragus:

- Light-headedness
- Fatigue/tiredness
- Mood changes
- Neck pain
- Tooth pain
- Pain/local skin irritation due to attachment of the device ear clips
- Tingling sensation due to the use of the device
- Palpitations

AEs will be recorded in the medical notes and on the appropriate AE pages of the CRF corresponding to the visit or interaction with the study team. Serious adverse events (SAEs) require expedited reporting to the device manufacturer (Afferent Medical Solution Ltd) and the Sponsor or designee regardless of relationship to study device or study procedure (refer for more information to

Investigators Brochure 9.3). All those will be informed as soon as possible and within 24 hours of the Investigator/ Investigation site staff become aware of the event. Potential interactions with other therapies any Device related SAEs are not anticipated. However, if they occur, the Principal Investigator and Investigation site will follow Afferents SOPs for reporting and managing them. Please see CIP section 13 for further information.

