# 11.0 Safety Reporting

# 11.1 Site investigator assessment

The Principal Investigator is responsible for the care of the participant, or in their absence an authorised medic within the research team is responsible for assessment of any event for:

- Seriousness
   Assessing whether the event is serious according to the definitions given in section Error!

   Reference source not found...
- Causality
  Assessing the causality of all serious adverse events in relation to the study treatment according to the definition given. If the SAE is assessed as having a reasonable causal

relationship with the investigational device, then it is defined as an ADE.

Expectedness

Assessing the expectedness of all ADEs according to the definition given. If the ADE is unexpected (as per the risk analysis or other Reference Safety Information (RSI) document), then it is a USADE.

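### Protocol 11.3 requires all adverse events on the CRF and then excludes the non-serious ones, so the adverse event totals in SAP Table 7 may be incomplete

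*Protocol*

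**What the plan says.** **Protocol 11.3** opens with a rule that has no seriousness limit: all AEs and ADEs are to be documented in the "medical notes or other source data documents and the CRF". Two sentences later it says: "Once assessed, if the AE is not defined as SERIOUS, will not be recorded as an AE on the CRF".

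**Protocol 10.12** covers device-specific events: "Any device-specific adverse events (AEs) will be recorded in the patient medical records and eCRF". Further down it states a rule without that restriction: "AEs will be recorded in the medical notes and on the appropriate AE pages of the CRF". Serious AEs are dealt with in the sentence after that. Its list of anticipated side effects includes "Pain/local skin irritation due to attachment of the device ear clips", as well as light-headedness, fatigue, neck pain and palpitations.

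**Protocol 11.7** asks the Chief Investigator to oversee the non-serious AEs that appear on the case report forms.

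**SAP section 5, Safety analyses**, presents both AEs and serious AEs as number and percentage by arm. Other AEs are reported separately when their prevalence exceeds 5% of all participants. **SAP Table 7** has rows for patients with at least one AE, total AEs, cardiac arrhythmia, local skin irritation and Other. No row is limited to serious events.

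**The concern.** The two sentences in 11.3 give opposite instructions for the same event, and no passage says which prevails. A research nurse who reads the second would leave a non-serious AE off the AE page. One who reads the first, or 10.12, would enter it.

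The Table 7 totals would then count all AEs, only serious ones, or a mixture, depending on who entered the data. This is a phase IIa device trial described as a pilot for a larger efficacy trial (Protocol 13.1), so its tolerability results should be readable. They are not if a low count cannot be told apart from events that were never entered.

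**Working it through.** The plan states no figure on this point, so the check is a comparison of texts. The SAP names Protocol version 3.0 as its reference, which is the version reviewed, so the conflict is not a version mismatch.

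1. **Within 11.3.** Take a non-serious AE. The first sentence sends it to the CRF; the later sentence keeps it off the CRF as an AE. Both cannot be followed.
2. **11.3 against 10.12.** One might read the later sentence as moving the event to some other CRF field. That does not help, because 10.12 names the AE pages. Nor is AE there shorthand for serious AE, since serious events have their own sentence.
3. **11.3 against 11.7.** If non-serious AEs are not entered as AEs, the Chief Investigator's review of them has little or nothing to work on.
4. **11.3 against the SAP.** The SAP presents AEs alongside serious AEs, and Table 7 counts any AE.
5. **Route into the analysis.** Protocol 15.5 exports the analysis dataset from the study database. Under 11.3 a non-serious AE would still be in the medical notes, but no step is planned to retrieve it from there for Table 7.
6. **Which rows are exposed.** Ear irritation has other routes: 10.12 sends device-specific events to the eCRF, and 14.5 says ear irritation, pain and dermatitis will be recorded, without naming the form. Arrhythmias in the first 24 hours are a secondary endpoint (2.3.2, Appendix A) and are collected separately (6.6). That leaves patients with at least one AE, total AEs, and Other.
7. **Sensitivity of the Other rule.** Assume all 36 participants are in the denominator and prevalence means participants with that event. The threshold is 0.05 × 36 = 1.8. One participant is 1/36 = 2.8%, below it; two are 2/36 = 5.6%, above it. If exactly two participants had an event, one unrecorded case would remove it from separate reporting. This shows how few omissions could matter, not how many to expect.

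**The case against.** The strongest defence is that 10.12 is the specific rule and 11.3 the general one. Section 10.12 is headed as dealing with device-specific events. On that reading those events go to the eCRF whatever their seriousness, and the later sentence of 11.3 governs only the rest. Section 11.7 and the skin irritation row then fit. There are further safeguards. Section 6.6 lists a safety review at baseline, during the procedure, at 24 hours and at day 7. Section 15.2 says the eCRF holds the safety events needed for analysis. The medical notes keep everything.

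Much of this stands as mitigation, and it narrows the exposed group to non-serious events that are not device-specific. It does not remove the contradiction. The opening rule of 11.3 still covers all AEs, 10.12 also deals with serious events whatever their relation to the device, and the Table 7 totals are not restricted to device-specific or serious events. The safety review is listed without saying where non-serious findings are entered.

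Three stronger readings are tempting but not supported:

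- **Ear irritation and arrhythmias will be lost.** Both have the other routes described above. Section 11.4 says atrial fibrillation and flutter will be recorded, as predictable outcomes. What remains is a labelling question: whether they count in the cardiac arrhythmia row.
- **11.3 leaves a gap at the start of reporting,** because it names both the screening visit and consent. Section 6.1 places consent within Visit 1, so the two largely coincide, and the device is applied only afterwards.
- **The loss can be sized from the 3/86 ear irritation rate in Protocol 1.0.** That rate describes the event with the best protection, not the exposed group.

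**Conclusion.** The contradiction in 11.3 is certain from the current text, and the later sentence is the one out of line with 10.12, 11.7 and the SAP. The consequence is conditional: if staff follow that sentence, the two Table 7 totals and the Other row could be incomplete, and a low count could not be interpreted.

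The size cannot be given. The documents report no rate for non-serious AEs that are not device-specific, and the CRF and Data Management Plan are not among them, so it cannot be checked which rule the form follows. A reader might infer that under-recording has happened or will happen; the documents show only that the instructions permit it. They also give no ground for saying that one arm would lose more events than the other. The primary endpoint and serious AE reporting are not touched. The text should be corrected, but the trial's main result does not depend on it.

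**What to change.** 1. **Protocol 11.3:** delete the sentence that excludes non-serious AEs. State one rule: all AEs and ADEs, serious or not, are recorded on the existing CRF AE page, with seriousness and severity, up to day 7. This agrees with the opening of 11.3 and with 10.12, 11.7 and the SAP.
2. **SAP Table 7:** name the data source for each row, and say whether atrial fibrillation or flutter recorded under Protocol 11.4 counts in the cardiac arrhythmia row.

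Serious-only capture of AEs that are not device-specific would also be coherent. If the sponsor intends that, the opening of 11.3, 10.12, 11.7 and Table 7 must be aligned with it, and Table 7 labelled so that readers know what the totals leave out.

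The cost is minor wording in the protocol and SAP, plus extra entry on an AE page that already exists, for 36 patients over seven days. The amount of entry cannot be estimated because the documents give no overall AE rate; in acute stroke patients it may not be trivial.

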# 11.4 Adverse events that do not require reporting

Refer to section 10.12 for more details on anticipated side effects and their reporting. Any neurological deterioration (including coma), seizures and atrial fibrillation/flutter are common AEs following ischaemic stroke, so will be recorded as predictable outcomes related to the primary presenting pathology.

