#### 1.3 Assessment and management of risk

The only established risk of the procedure is local skin irritation to the outer ear region. There is a theoretical risk of autonomic-induced cardiac arrhythmias, but there are no reports from an extensive literature search. The battery operated device bears no electrical risk.(PMID: 34801224) There are no other neurological side effects that have been reported. Our recent experience in 86 patients admitted with orthopaedic trauma who underwent TAN for pain control demonstrate no risks other than a local sensation of tingling in the outer ear and mild, inconsequential skin irritation that did not require any clinical intervention/therapy. The device is located well away from implanted pacemakers so pose no risk to other indwelling electrical devices. The overall risk-benefit ratio is very low, less than pharmacological interventions in stroke for blood pressure control.

VANS v3.0 20.04.2023 Page 8 of 44

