#### 6.5 Unblinding

Unblinding a participant's treatment is strongly discouraged as it can compromise the integrity of the trial. However, unblinding may be necessary on rare occasions for medical or safety reasons that can affect clinical management. In this trial, unblinding may be required if a patient experiences a cardiac arrhythmia of concern to attending clinicians. The PI or assigned delegate must determine the necessity of unblinding, and contact the study coordinating team for further discussion. Healthcare professionals will be provided with emergency contact details of the research team to quickly unblind a participant if knowledge of the treatment assignment is essential for optimal medical treatment. A 24-hour emergency unblinding procedure will be available, and participants will receive a trial card with emergency contact details. Unblinding requests are expected to be rare as the rescue treatment should not depend on the treatment group allocation.

To ensure the safe unblinding of information in case of a safety concern, we will store unblinding details in a securely locked cupboard that can be accessed by the research/clinical team with prior discussion and approval from the PI or their designated representative. The cupboard will be accessible at all times. Unblinding information will be contained in opaque sealed envelopes that will be labelled with the corresponding stimulator box number and contain treatment group allocation (stimulation or sham) inside. The Statistician will be responsible for inserting the treatment group information and sealing each envelope, which will be witnessed and verified by an independent staff member not involved in the trial. This process will ensure that the treatment group allocation cannot be viewed without opening the sealed envelope. To enhance the security and confidentiality of the unblinding process, each envelope will be signed by the Statistician on the back, and they can be examined at the end of the trial to verify that none of them have been tampered with. The envelopes will be kept in a designated folder that is labelled clearly, and this folder will be stored in a securely locked cupboard that can be accessed at any time of the day. The Statistician and the witness will sign a file note that outlines the process used to create and seal the envelopes.

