# 11.6 Notification and reporting of Serious Adverse Events (SAEs), and Unexpected Serious Adverse Device Events (USADEs)

Refer to Investigator Brochure sections 9.2 and 9.3. AllSAEs that are considered to be 'related' and 'unexpected' are to be reported to the Sponsor and the Sponsor's representative within 24 hours of learning of the event. The SAEs and reportable device deficiencies must be reported from consent until the participant's last follow-up visit. All Serious Adverse Event (SAEs) and Unexpected Serious Adverse Device Events (USADEs) will be recorded in the participants' notes, the CRF, the Sponsor SAE form and reported to the device manufacturer (Afferent Medical Solution Ltd) and the Sponsor (administered by the Joint Research Management Office or agreed representative) (except those specified in this protocol as not requiring reporting). SAE form and reported to the Sponsor (Joint Research Management Office via mailbox at [contact]), Afferent Medical Solution Ltd. ([contact]) within 24 hours of the Chief Investigator or Sub-Investigator(s) becoming aware of the event. Nominated Sub-Investigators (as listed on the Investigator at the participating sites. SAEs and reportable device deficiencies will be reported from consent until the participant's last follow-up visit.

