HF, power				
HF, peak				
DFA1				
DFA2				

Table 6. Process/ exploratory measures.

	ACTIVE	SHAM
NIH Stroke Scale (NIHSS) 24h after mechanical thrombectomy (delta change from admission)		
Health status 7 days after mechanical thrombectomy.		
Alive		
Troponin change from admission (delta change from admission)		

Table 7:Adverse events

Adverse Events - no. (%)	active	sham
Patients with ≥ 1 adverse event		
Total number of adverse events		
Type of adverse event		
Cardiac arrythmia		
Local skin irritation		
Other

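### AF/flutter is exempt from event reporting although arrhythmia is the device's named theoretical risk, and the AE and SAE rules conflict, so the SAP's arrhythmia row can under-count

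*Protocol*

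**What the plan says.** **Arrhythmia as a device risk.** Protocol 1.3 gives skin irritation as the only established risk and adds: "There is a theoretical risk of autonomic-induced cardiac arrhythmias". No other risk is called theoretical. Section 6.5 says that "unblinding may be required if a patient experiences a cardiac arrhythmia of concern to attending clinicians". Section 10.11 says the device is not used in a treatment period in which arrhythmia develops. Section 10.12 lists palpitations among the anticipated side effects.

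**The exemption.** Section 11.4 is headed "Adverse events that do not require reporting". It states that "seizures and atrial fibrillation/flutter are common AEs following ischaemic stroke, so will be recorded as predictable outcomes" of the presenting stroke. Section 11.6 requires SAEs and USADEs to be recorded and reported, "except those specified in this protocol as not requiring reporting".

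**SAE scope.** Section 10.12 requires expedited reporting of SAEs "regardless of relationship to study device or study procedure". Section 11.6 opens more narrowly: SAEs judged both related and unexpected "are to be reported to the Sponsor and the Sponsor's representative within 24 hours of learning of the event". It then widens to all SAEs, minus the exempt ones.

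**AE recording.** Section 11.3 first sends every AE to the notes and the CRF, then says that a non-serious one is not entered on the CRF as an AE. Section 10.12 refers to AE pages of the CRF. Section 11.7 has the Chief Investigator review non-serious AEs reported on the CRF.

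**Tabulation.** SAP Table 7 has a row "Cardiac arrythmia" under type of adverse event, by arm. Neither the table nor the SAP's safety text names the source or the time window.

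**The concern.** A high background rate of AF after stroke is a reason to compare arms. It does not show that no individual case is device-related. Section 11.4 assigns the cause by category, while 11.1 asks the investigator to assess causality for every SAE. The protocol's background also lists reduced AF as a hoped-for benefit, so the count matters in both directions.

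The conflicting rules mean that staff could treat the same event differently, depending on which section they follow. A safety table built from such records would mix true absence with non-recording. Section 14.0 plans no safety analysis at the outset, so the tabulation by arm at the end is the main planned place where an imbalance would show.

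**Working it through.** There is no stated figure to reproduce: the documents give no arrhythmia rate and no power for safety. The check sets the rules side by side and applies them to specific events.

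**Step 1. Is a serious event reportable within 24 hours?**

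| Event | 10.12 | 11.6, opening rule | 11.6, later rule |
|---|---|---|---|
| Serious AF, judged unrelated | yes | no | exempt through 11.4 |
| Serious AF, judged related and unexpected | yes | yes | exempt through 11.4 |
| Serious AF, judged related but expected | yes | no | exempt through 11.4 |
| Serious arrhythmia other than AF/flutter, judged unrelated | yes | no | yes |

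No row gets the same answer from all three rules. The exception in 11.6 is attached to a sentence that covers USADEs as well as SAEs, so even an event judged device-related is not clearly outside it.

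**Step 2. Is non-serious AF on the CRF as an AE?** The opening of 11.3, the AE pages in 10.12 and the review in 11.7 imply yes. The later sentence of 11.3 says no. Section 11.4 says it is recorded as an outcome of the stroke, without saying where. The 11.3 sentence applies to any non-serious arrhythmia, so deleting 11.4 alone would not restore those events to the AE records.

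**Step 3. What else captures arrhythmia?**

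- *0 to 24 hours:* clinically recorded arrhythmias are a secondary endpoint (2.3.2, Appendix A) and are collected in both arms (6.6). AF/flutter is not excluded. SAP Table 2 has an arrhythmia row by arm, under clinical management.
- *24 hours to day 7:* the SAP's organ-dysfunction outcome runs for seven days and includes arrhythmias. The protocol's day-7 list in 6.6 has mortality, hospital stay and a safety review, with no arrhythmia item. The schedule in 6.2 adds a record review and a heart rate and blood pressure safety review, without defining their content. Organ dysfunction is absent from the SAP's list of secondary analyses and has no dummy-table row of its own.

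**Step 4. Illustration of size.** Inputs from the documents: 36 participants allocated 1:1, so 36 / 2 = 18 per arm. Assumed inputs: the true AF/flutter rates, the share still recorded as AEs, and Table 7 being filled from AE records. Expected AF/flutter patients in the row = 18 × rate × share retained.

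| Assumed rates, sham v active | True | Half retained | None retained |
|---|---|---|---|
| 10% v 20% | 18 × 0.10 = 1.8 v 18 × 0.20 = 3.6 | 0.9 v 1.8 | 0 v 0 |
| 10% v 30% | 18 × 0.10 = 1.8 v 18 × 0.30 = 5.4 | 0.9 v 2.7 | 0 v 0 |

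In the second case the difference between arms falls from 3.6 patients to 1.8, or to none. These counts concern AF/flutter only; 11.4 does not exempt other arrhythmias. If Table 7 is filled from the arrhythmia endpoint items instead, nothing is lost within 24 hours.

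**The case against.** Leaving events expected from the presenting disease out of expedited reporting is a declared choice with a stated reason. The risk in 1.3 is arrhythmia in general, and that section says a literature search found no reports; only AF/flutter is exempt. Section 11.4 still says these events are recorded, and the 24-hour endpoint covers the period of the procedure. The opening rule of 11.6 concerns reporting to the sponsor, not what is tabulated. All of this stands, and it limits the point.

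A reader might go further in four ways that the documents do not support:

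- *Table 7 will under-count.* This depends on its source, which its layout suggests but the SAP does not state.
- *AF/flutter after 24 hours is captured nowhere.* The SAP's seven-day organ-dysfunction outcome includes arrhythmias. What is missing is a matching collection item and table.
- *An excess would not reach the IDMC.* Section 23.3 has the committee review unblinded trial data, and arrhythmias are among the data collected.
- *AF is the commonest arrhythmia here.* The protocol says only that these events are common.

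The same exemption covers seizures and neurological deterioration. The documents name no device risk there, and 1.3 reports no other neurological side effects, so removing those two would be closer to preference.

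What the objection does not answer is the lack of any exception for serious, new-onset or possibly device-related AF/flutter, and the direct conflicts between 10.12, 11.3, 11.6 and 11.7.

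**Conclusion.** The point holds as a conflict between reporting rules that bears on the trial's one named theoretical risk. Serious AF/flutter is reportable under one section and exempt under another. Non-serious arrhythmia is both on and off the CRF as an AE. The Table 7 arrhythmia row can under-count, on the assumption that it draws on AE records; the possible loss of AF/flutter cases runs from none to all, depending on which rule staff follow. The expected counts above rest on assumed rates and show only the scale with 18 per arm. Within 24 hours the endpoint data are a safeguard. From 24 hours to day 7, the SAP specifies an outcome for which the protocol lists no specific item. This should be changed, but it does not affect the primary analysis.

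**What to change.** 1. Reconcile Protocol 10.12, 11.3, 11.4, 11.6 and 11.7 into one rule stating which AEs are recorded on the CRF and which SAEs are reported, to whom and by when.
2. Narrow the 11.4 exemption so that AF/flutter that is new, or worse than baseline, after first device use is recorded with its onset relative to stimulation and assessed for seriousness and causality.
3. Add an arrhythmia item to the day-7 list in 6.6, to match the SAP's seven-day outcome.
4. State in the SAP the source and time window of the Table 7 arrhythmia row, and show AF/flutter by arm.

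Items 1 and 2 are needed together: without settling 11.3, narrowing 11.4 would still leave non-serious AF off the CRF as an AE. The cost is a protocol and SAP wording change and a few extra event forms in 36 patients.
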